2.2 Plerixafor

Plerixafor is a reversible inhibitor of the binding of stromal cell derived factor - 1α (SDF- 1α), also known as chemokine (C-X-C motif) ligand 12 (CXCL12) to its cognate receptor chemokine (C-X-C motif) receptor 4 (CXCR4).

The FDA has not approved the drug or biologic for treatment of this indication to date.

2.3 Rationale

Our experimental studies suggest that post-irradiation tumor recurrences can be prevented or markedly delayed by blocking the influx of circulating proangiogenic cells including CD11b+ monocytes and endothelial cells into the tumor [9, 10]. Perixafor is a reversible inhibitor of binding and would prevent or markedly delay the influx of proangiogenic cells thereby preventing post-irradiation tumor recurrences in glioblastoma.

Version #11, Date: 04-29-2015 Page 7 of 52

2.4 Study Design

For clinicaltrials.gov and Stanford Clinical Trials Directory compliance

- State the primary purpose for the protocol:
 - o Treatment
- State the interventional model from these choices:
 - Single Group
- State the number of intervention arms.
 - o One
- State whether the study will be masked (at least one party is unaware of the treatment)
 - o **Open**: no masking is used
- State whether the study is randomized.
 - o No
- State type of primary outcome or outcome that the protocol is designed to evaluate:

Safety (Phase I) Efficacy (Phase II)

Phase I

The Phase I is designed to evaluate safety. A total of 9 newly diagnosed patients will be enrolled within four weeks of surgery (biopsy, partial resection or gross total resection). In order to minimize the chances for local angiogenic migration into the irradiated field, irradiation will be administered to the area encompassed by T2 FLAIR imaging plus a 2 cm margin to 46 Gy with a focal boost to the enhancing area to 60 Gy over a six-week period. Temozolomide 75 mg/M²/d starting the day of radiotherapy will be administered for 42 days concurrent with irradiation. Eight days prior to irradiation completion, patients will have a PICC line placed. Seven days prior to irradiation completion, the continuous infusion of Plerixafor will be initiated using a step-wise dose escalation based on the modified toxicity probability interval (mTPI) method. All treatments will start one week prior to completion of radiotherapy with concurrent temozolomide for patients with newly diagnosed glioblastoma. This dose escalation study begins with an intermediate dose of 200 µg/kg per day for four weeks. The first 3 patients will be enrolled at this starting dose. Enrollment within a dose level will be staggered so that there is at least 1 week between patients. If tolerability and safety is established after the 4 week treatment period, then the fourth patient will be enrolled at the higher target dose of 400 µg/kg per day for four weeks. We will wait one week after the last infusion at one dose level before proceeding to the next dosage level.

If a patient experiences a DLT, then s/he will be removed from study and the next patient treated at the lower dose level as dictated by the mTPI table.

Once the infusion phase is completed, patients will then receive adjuvant temozolomide in standard monthly dosages (i.e., 150 mg/m² x 5 days), beginning at day 35 after finishing XRT (to ensure no overlap with Plerixafor).

Version #11, Date: 04-29-2015 CONFIDENTIAL

Phase II

If in the Phase I, patients achieve the highest AUC level (i.e., $400 \mu g/kg$ per day for 4 weeks) without significant toxicity, we will then conduct a lead-in Phase II study wherein an additional 20 patients will be enrolled so that efficacy (i.e., PFS 6) can be measured. There will be no delay between enrolling patients in this group and multiple patients can be enrolled and treated at the same time.

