4. TREATMENT PLAN

4.0.1 Screening

The following procedures will be performed for all potential subjects at the Screening visit to be conducted 7 days prior to the start of Plerixafor infusion (+/- 3 days):

- Written informed consent must be obtained from the patient prior to performance of any study-specific tests or procedures
- Confirm Eligibility Criteria
- Post-operative, contrast-enhancing imaging
- Demographics: birth date, race/ethnicity and gender at birth
- Medical history
- Cancer history
- Physical Exam
- KPS
- Concomitant medications
- Vital Signs (including height and weight)
- ECG
- Laboratory tests: CBC with differential, Comprehensive Metabolic Panel (including: sodium, potassium, chloride, CO2, glucose, creatinine, urea nitrogen, calcium, protein, albumin, total bilirubin, ALK Phosphatase, AST, ALT and magnesium), Pregnancy Test (only for women of child bearing potential), INR, PTT, and Urinalysis with microscopic

Day 0 (within 3 days of beginning of Plerixafor infusion):

• Placement of the PICC line and infusion pump

Day 1 must occur 7 days (+/- 3 days) prior to the completion of XRT:

- Physical Exam
- KPS
- Vitals: pre-dose, 15 min (+/- 5 min), 30 min (+/- 5 min), 1 hr (+/- 15 min), 2 hrs (+/- 15 min) 3 hrs (+/- 30 min) and 6 hrs (+/-30 min) after the start of Plerixifor infusion
- Laboratory tests: CBC with differential, Complete Metabolic Panel (including: sodium, potassium, chloride, CO2, glucose, creatinine, urea nitrogen, calcium, protein, albumin, total bilirubin, ALK Phosphatase, AST, ALT and magnesium), Troponin
 - o Patients may proceed with the Plerixafor infusion even if the Day 1 ANC and platelets no longer meet inclusion criteria 3.1.7 due to the concurrent temodar and radiation and at the investigator's discretion; Thrombocytopenia should be ≤ grade 2
- Phase I only: SDF-1 levels (within 24 hours prior to the start of infusion)
- Phase I only: Samples for PK analysis will be drawn prior to and 1 hour (+/- 10 min) after start of the infusion of Plerixafor

Version #11, Date: 04-29-2015 Page 23 of 52

- ECGs: prior to the start of the Plerixafor infusion and 6 hours (+/- 30 min) after
- Phase I only: ECG 3 hours (+/- 30 min) after start of Plerixafor infusion
- Begin Plerixafor infusion in outpatient unit.
- Observe patients for 6 hours after the start of the Plerixafor infusion
- Patient will be discharged home after at least 6 hours with infusion pump.

Day 4 (+/- 2 days) for Phase I patients only

- Vitals

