- Laboratory tests: CBC with differential, Complete Metabolic Panel (including: sodium, potassium, chloride, CO2, glucose, creatinine, urea nitrogen, calcium, protein, albumin, total bilirubin, ALK Phosphatase, AST, ALT and magnesium),
- ECG

Weekly following the start of the Plerixafor infusion through the end of infusion (+/- 3 days):

- Physical Exam
- KPS
- Vitals
- ECG
- Laboratory tests: CBC with differential, Complete Metabolic Panel (including: sodium, potassium, chloride, CO2, glucose, creatinine, urea nitrogen, calcium, protein, albumin, total bilirubin, ALK Phosphatase, AST, ALT and magnesium)
- Phase I only: PKs
- Change infusion bag of Plerixafor
- Review concomitant medications and adverse events
- On the last day of infusion, an SDF level will be checked (+/-1 week)
- Biweekly following the start of Plerixafor infusion through the end of infusion (+/- 3 days):Laboratory tests: Troponin

4 weeks after the end of XRT (+/- 7 days):

- MRI brain with and without contrast
- Start monthly TMZ

Concomitant medications and adverse events will be followed up until 30 days after the end of the Plerixafor infusion.

Investigator will manage monthly TMZ per their standard practice. Follow up MRIs will be done per standard of care (approximately every 8-12 weeks).

6 months after the start of XRT (+/- 2 weeks):

• MRI brain with and without contrast

Post-Progression Follow-Up:

Unless a patient has specifically withdrawn consent to be followed for survival, he or she will be

Version #11, Date: 04-29-2015 Page 24 of 52

contacted (by phone or clinic visit) every 12 weeks (+/- 2 weeks) following disease progression to collect data regarding survival status and subsequent anticancer therapy. Follow up will continue for either 5 years or until death, withdrawal, lost to follow up, or study termination.

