6.1 Dose Limiting Toxicities

DLT is defined as any hematologic or non-hematologic AE grade ≥3 with a suspected causal relationship to Plerixafor (including including ECG changes indicative of ischemia, ventricular tachycardia).

- Patients will be monitored for DLTs for 5 weeks from the start of the Plerixafor infusion.
- DLT's in the first cohort may occur before or after 14 days. If a DLT occurs in weeks 3 or 4 of treatment, we will treat next patient with a dose of 200 μg/kg/d x2 weeks. If a DLT occurs from the start of treatment through the second week of treatment, we will

Version #11, Date: 04-29-2015 Page 27 of 52

treat next patients at a dose of 100 μ g/kg/d x 4 weeks. If a patient experiences a DLT, the infusion will be discontinued. The next patient treated at the lower dose level as dictated by the mTPI table. If an early dose limiting toxicity occurs at lowest dose level (200 μ g/kg/d x 2 wk or 100 μ g/kg x 4wks) then the protocol will be stopped at that point.

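### Section 2.4 starts adjuvant temozolomide at day 35 after XRT, but 4.0.1 permits days 21-35, and its early dates fall inside the 5-week DLT window

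*Combined protocol and SAP*

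**What the plan says.** Section 2.4, under Phase I, makes the end of the infusion a condition: "Once the infusion phase is completed, patients will then receive adjuvant temozolomide". It gives the start as "beginning at day 35 after finishing XRT (to ensure no overlap with Plerixafor".

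Section 4.0.1 has a visit at "4 weeks after the end of XRT (+/- 7 days". One of its two items is "Start monthly TMZ"; the other is a brain MRI. The section later adds "Investigator will manage monthly TMZ per their standard practice". It does not repeat the condition in 2.4.

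The calendar in section 9 puts temozolomide and the first MRI in a Day 35 (±7) column. It does not say what that day is counted from; the columns to its left are counted from infusion Day 1.

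Two further rules fix the geometry. Section 4.0.1 states "Day 1 must occur 7 days (+/- 3 days) prior to the completion of XRT". Section 6.1 states "Patients will be monitored for DLTs for 5 weeks from the start of the Plerixafor infusion", and it counts as a DLT any grade 3 or higher event, haematologic events included, that is suspected to be related to Plerixafor.

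**The concern.** Section 2.4 gives a reason for its date: to keep adjuvant temozolomide clear of Plerixafor. Section 4.0.1, which a site would follow day to day, permits dates up to two weeks earlier. No text reconciles the two.

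The Phase I question is toxicity in 9 patients, and attribution to Plerixafor decides what counts as a DLT. Low blood counts have more than one possible cause here. Section 4.0.1 lets the infusion proceed even when the "Day 1 ANC and platelets no longer meet inclusion criteria 3.1.7 due to the concurrent temodar and radiation". Section 7.1 lists thrombocytopenia among the serious events of the earlier 10-day continuous-infusion study. If a new temozolomide cycle starts before the DLT window closes, a late grade 3 or higher event has one more candidate cause, of the kind that 2.4 set out to avoid.

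A single call can matter. In Table 12.1, with three patients at a dose, 0 DLTs gives E, 1 gives S and 2 gives D.

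**Working it through.** **Inputs.** Infusion start: 7 ±3 days before XRT ends (4.0.1). Infusion length: 4 weeks, or 2 weeks at one dose level (5.1). DLT window: 5 weeks from infusion start (6.1). Temozolomide start: XRT day 35 (2.4) or XRT days 28 ±7 (4.0.1).

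**Convention.** XRT ends on day 0. The infusion starts on day s = -10, -7 or -4. A 4-week infusion is complete at s + 28 and the DLT window closes at s + 35. A temozolomide date d overlaps if d is less than that value. The 4.0.1 dates are d = 21 to 35, which is 15 dates.

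| Infusion start s | 4-week infusion complete | DLT window closes | 4.0.1 dates before window close | 4.0.1 dates before infusion complete |
|---|---|---|---|---|
| -10 | 18 | 25 | 21-24: 4 of 15 | 0 |
| -7 (nominal) | 21 | 28 | 21-27: 7 of 15 | 0 |
| -4 | 24 | 31 | 21-30: 10 of 15 | 21-23: 3 of 15 |

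If the closing day itself is counted as inside the window, the window counts become 5, 8 and 11.

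**Target dates.** The 2.4 date, day 35, is later than 25, 28 and 31, so it clears the window in every case. The 4.0.1 target, day 28, falls as the window closes at nominal start. It is 3 days early only for the latest start (31 - 28 = 3).

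**Calendar.** Counted from infusion Day 1, Day n is XRT day s + n - 1. Days 28-42 are then s + 27 to s + 41, or XRT days 20-34 at nominal start, within a day of 4.0.1. On this reading Days 28-35 (8 of 15) precede window close at Day 36, and Day 28 (1 of 15) precedes completion of a 4-week infusion.

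**Residual drug.** Section 2.5 gives a median terminal half-life of 8.6 hours (range 8.1-11.1) after continuous infusion. Five half-lives are 5 × 8.6 = 43 hours, or 1.8 days (40.5-55.5 hours, 1.7-2.3 days). A 2-week infusion ends at s + 14 = 4, 7 or 10, so by XRT day 21 it has been off for 17, 14 or 11 days. Most overlapping dates therefore raise a question of attributing late events, not of exposure to both drugs together.

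**Chance of detection.** The calendar's last blood count is Day 29 (±3), so Day 32 at the latest. XRT day 21 is study Day 21 - s + 1: Day 32, 29 or 26 for s = -10, -7 or -4. From the earliest permitted temozolomide date to the last possible protocol count is thus 0, 3 or 6 days.

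**The case against.** The strongest reply is that the overlap belongs to the edge of a tolerance window. At the 4.0.1 target and nominal infusion start, temozolomide begins 7 days after a 4-week infusion ends and as the DLT window closes, so the stated aim of 2.4 is met. The sequencing condition in 2.4 also rules out giving both drugs at once. All of this stands, except that the condition protects only the infusion and not the week of DLT follow-up after it.

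The harm also needs temozolomide to produce a grade 3 or higher event within the days that remain, and the documents give no time to onset. Protocol blood counts have almost stopped by then. Standard-of-care counts might show a fall, but the documents do not specify them. Concurrent temozolomide is present by design, and investigators judge causality in any case. These points stand and limit the size of the problem.

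The effect on dose decisions is also less settled than Table 12.1 alone suggests. At the highest dose E means the same dose, so 0/3 and 1/3 lead to the same action; 1/4 and 2/4 are both S, as are 2/6 and 3/6. The separate timing rules in 6.1 and 12.1 name an action for DLTs in weeks 1-2 and weeks 3-4 but not in week 5, where most of the overlapping dates fall.

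A reader might infer three conflicting schedules. The documents support two targets: the calendar, read from Day 1, sides with 4.0.1, and 2.4 and 4.0.1 share day 35, so a site starting then complies with both.

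**Conclusion.** The inconsistency is real, and the day counts follow directly from the stated windows. Under 4.0.1, 4, 7 or 10 of 15 permitted dates precede DLT-window close, and 0, 0 or 3 precede the end of a 4-week infusion if the condition in 2.4 is not applied. These are counts of permitted dates, not of expected patients or DLTs.

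The consequence is avoidable attribution uncertainty for late events in the 9 Phase I patients. It cannot be quantified and is probably small. A reader might go further and infer that the plan routinely doses temozolomide inside the DLT window, or that DLT calls and the selected dose will be distorted. The documents support neither: the nominal dates do not overlap, no onset time is given, and few protocol counts would catch a late fall. The DLT argument also gives no reason to delay the 20 Phase II patients.

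The conclusion rests on the window closing 35 days after infusion start and, for the calendar only, on counting its column from infusion Day 1. The change is still worth making, because it governs when a drug may be given in a phase whose endpoint is DLT and it costs very little.

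**What to change.** Add one sentence to 4.0.1 and to the calendar: adjuvant temozolomide may not start until the Plerixafor infusion has ended and, in Phase I, until that patient's 5-week DLT window has closed. This alone removes the overlap.

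For consistency, use one target date in 2.4, 4.0.1 and the calendar; day 35 after XRT is the one 2.4 already specifies. State what the calendar column is counted from.

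As an editorial correction, give the first post-radiation MRI one date. Section 4.0.1 has 28 ±7 days and 10.2.4 has 35 ±3 days after XRT.

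Cost: with the day-35 target, the first adjuvant cycle starts up to about a week after the 4.0.1 target (35 - 28 = 7 days) in some patients. If day 28 were kept with the added condition, the delay past that target would be at most 3 days, and only for Phase I patients whose infusion started later than nominal. The condition also narrows the discretion that 4.0.1 leaves to investigators. No procedure is added.

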2.5 Correlative Studies Background

We have recently developed and validated with several transplanted tumors in mice (including intracranially implanted human GBM) a new paradigm for the treatment by radiotherapy of solid tumors: Namely that post-irradiation tumor recurrences can be prevented or markedly delayed by blocking the influx of circulating proangiogenic cells- CD11b+ monocytes and endothelial cells - into the tumor [9, 10]. The significance of our findings is illustrated by the fact that our strategy to prevent GBM recurrence has been highlighted in recent commentaries in prominent biomedical journals [11]. Furthermore, our findings of the importance of CD11b+ monocytes and/or macrophages to tumor response to irradiation have now been confirmed by others [12].

Our findings of relevance to the present proposal are summarized as follows:

• We have shown that the clinically approved drug Plerixafor (AMD3100), which inhibits the interaction of stromal cell-derived factor-1 (SDF-1, CXCL-12) with its receptor, CXCR4, on bone marrow derived CD11b+ monocytes (which are highly proangiogenic) [13] both inhibits the radiation-induced influx of the CD11b+ monocytes and prevents tumor recurrence following single or fractionated doses of irradiation (Figs 1A,C). We have confirmed the importance of the SDF-1/CXCR4 pathway for tumor recurrences by demonstrating that neutralizing antibodies to CXCR4 also inhibit tumor recurrence after irradiation (Fig 1D). In addition we have shown that neutralizing antibodies to CD11b+ monocytes can inhibit the recurrence of a human head and neck cancer in nude mice, as well as demonstrating that tumors in mice genetically deficient in CD11b+ cells are radiosensitive [10].

- We have demonstrated that blockage of angiogenesis following irradiation with the anti-VEGFR2 neutralizing antibody DC101 is not as effective in potentiating the response to irradiation as is AMD3100 either by tumor recurrence or by inhibition of tumor blood flow following irradiation (Figs 1E,F).
- We have shown that radiation selectively depletes the tumor vasculature thereby inducing tumor hypoxia and upregulating the transcription factor hypoxia inducible factor-1 (HIF-1), which in turn transactivates SDF-1, the key chemokine responsible both for the mobilization of bone marrow derived proangiogenic cells and their retention in the irradiated tumor. [9, 10].
- We have demonstrated the importance of CD11b+ monocytes in tumor recurrences after irradiation in patients by showing that, as in mice, GBM recurrences in patients following irradiation have higher levels of CD11b+ monocytes than prior to therapy (Fig 2).
- We have demonstrated that irradiated tumors express elevated levels of SDF-1 and this

Version #11, Date: 04-29-2015 Page 9 of 52

chemokine is found at higher levels in the plasma of rats and patients with irradiated brain tumors.

[figure not shown]

Figure 1. Inhibition of the interaction of SDF-1 with CXCR4 with AMD3100 prevents tumor recurrence post irradiation. A Growth curves of i.c. U251 by bioluminescent imaging (BLI) following whole brain fractionated irradiation (5 daily doses of 2 Gy starting on day 11 after transplantation) with AMD3100 (5mg/kg/day for 21 days) started immediately after the last irradiation, B. BLI images following fractionated irradiation (5 x 2 Gy) treated with or without AMD3100. (CD) Growth curves of i.c. U251 following a single dose of irradiation (15 Gy on day 22 following transplantation) treated with AMD3100 (21 day infusion); C) or treated with neutralizing anti-CXCR4 Ab (D), starting immediately following irradiation. E, growth curves of U251 i.c. tumor following 15 Gy irradiation treated with DC101. Arrow-heads indicate the treatment of DC101 (started immediately following irradiation and maintained for 21 days). F, AMD3100 is more effective than DC101 in reducing tumor blood flow by irradiation. Quantification of endothelial cells and functional vessels in U251 s.c. tumors following 15 Gy irradiation and combined with AMD3100 or DC101. Samples were taken 17 days after irradiation. Errors indicates S.E.M. **p<0.01, ***p<0.001 (versus IR). From Kioi et al.

[figure not shown]

Figure 2. CD11b+ cells are increased with GBM tumor recurrences in patients., Left: IHC staining for CD11b of GBM clinical samples both before treatment (primary) and after recurrence Right Significant increased levels of CD11b+ cells in the recurrent human GBMs compared to the untreated tumors. Quantification of CD11b based on IHC with CD11b staining. Ten of twelve samples showed increases of CD11b cells in recurrent GBMs (Error SEM). Bar; 50 μ m. From Kioi et al 12

Because the CXCR4 serves as a co-receptor, along with CD4, for the binding of human immunodeficiency virus type 1 (HIV-1) [17], initial Plerixafor clinical trials were conducted for the treatment of HIV-1 infection [18]. In follow-up to the observation that Plerixafor given to healthy volunteers and HIV-1 infected patients elicited increases in white blood cell (WBC) counts, studies have been done in healthy volunteers to assess the effect on circulating peripheral blood stem cells (PBSCs) [19]. Coincidentally, data emerged demonstrating that homing of CXCR4-expressing stem cells to bone marrow is regulated, at least in part, through a chemoattractant effect of SDF-1α that is produced locally by bone marrow stromal cells [20]. In fact, disruption of the SDF-1α/CXCR4 through G-CSF exposure [21] or with chemotherapy, results in the appearance of both mature and pluripotent cells in the systemic circulation. Unlike the modes of action of either chemotherapy or cytokine growth factors, however, Plerixafor exerts its effect on PBSC mobilization as a direct consequent of its antagonism of CXCR4 [22]. Subsequent PBSC mobilization studies have shown Plerixafor to have a synergistic effect on the number of circulating progenitor cells when administered with G-CSF in patients with non-Hodgkin lymphoma (NHL) and multiple myeloma (MM) [23, 24].

Pharmacokinetics of Plerixafor

The kinetics of dosing of Plerixafor was first explored in humans in a phase I bioavailability study in 17 healthy volunteers; 12 by intravenous (IV) infusion (three subjects each at 10, 20, 40, and 80 µg/kg), 5 by subcutaneous (SC) injection (two subjects at 40 µg/kg and three at 80 µg/kg) [25]. In this study, the C_{max} and $AUC_{0-\infty}$ demonstrated dose proportionality across the four dose levels. However, a higher Cmax for IV administration was noted compared to SC administration (IV: 292.8 ± 67.0 and 503.9 ± 29.6 , SC: 123.5 ± 27.9 and 238.3 ± 17.3) for the 40 and 80 µg/kg dose levels, respectively. The bioavailability of Plerixafor was determined to be 80-90%. The pharmacokinetic behavior of Plerixafor is characterized by elimination from the plasma in a bi-exponential manner with a terminal elimination half-life of approximately 3.5-5 hours following a single dose. Plerixafor absorption following subcutaneous administration is rapid and essentially complete, with peak plasma levels occurring within 0.5-1

hour of dosing. The exposure-response relationship of Plerixafor in mobilizing CD34 + cells when administered as a single agent was also independently explored at doses ranging from 80-320 μ g/kg in 32 healthy volunteers [26] and from 40–320 μ g/kg in 29 additional healthy volunteers [27]. In both studies, Plerixafor exhibited linear pharmacokinetics (PK) over the tested dose range (up to 320 μ g/kg), consistent with previously reported PK results. Plerixafor is extensively protein bound to both human serum albumin and 1-acid glycoprotein; however, protein binding does not appear to have a major influence on either antiviral activity, effect on stem cell mobilization or toxicity. Saturation of protein binding sites may occur at plasma Plerixafor concentrations in excess of those likely to be achieved in any ongoing or planned clinical studies.

The safety and the pharmacokinetics and pharmacodynamics of Plerixafor with G-CSF in patients with non-Hodgkin lymphoma (NHL) and multiple myeloma (MM) was also evaluated in a phase II, open-label, single-arm study [28]. The patients were given G-CSF (10 µg/kg/day SC) for 4 days in the morning and Plerixafor 240 µg/kg SC on the evening before each day of apheresis. The PK profile of Plerixafor was characterized in 13 patients (5 with NHL and 8 with MM) and, overall, parameters were comparable in the patients with NHL and those with MM. Plerixafor was rapidly absorbed after SC administration with no observable lag time, with peak plasma concentrations occurring 0.5 hour after administration in most patients. Plerixafor was rapidly cleared, with a median terminal half-life of 4.6 hours. The median maximum increase in the number of circulating cells from baseline was 4.2-fold (range, 3.0- to 5.5-fold); with the maximum fold increase occurring approximately 10 hours after Plerixafor injection for all patients. The Plerixafor PK and PD profiles in the study patients were consistent with those in healthy volunteers and support the current dosing regimen and timing of apheresis.

The primary route of elimination of Plerixafor is through the kidneys. A Phase I openlabel study in healthy subjects was conducted to evaluate the pharmacokinetic characteristics of Plerixafor in subjects with renal impairment [29]. All subjects received a single 240 µg/kg subcutaneous dose of Plerixafor. Subjects were stratified into 4 cohorts based on creatinine clearance determined from a 24-hour urine collection: control (>90 mL/min), mild renal impairment (51-80 mL/min), moderate renal impairment (31-50 mL/min), and severe renal impairment (<31 mL/min, not requiring dialysis). Eleven women (48%) and 12 men (52%), ranging in age from 35 to 73 years, were enrolled. Plerixafor clearance was reduced in subjects with renal impairment and was positively correlated with creatinine clearance. The mean area under the concentration-versus-time curve from time 0 to 24 hours postdose of Plerixafor in subjects with mild, moderate, and severe renal impairment was 7%, 32%, and 39% higher, respectively, than that in subjects with normal renal function. Renal impairment had no effect on maximal plasma concentrations. The safety profile was similar among subjects with renal impairment and controls. No renal impairment-related trends in the incidence of adverse events (AEs) were apparent. A Plerixafor dose reduction to 160 µg/kg in patients with a creatinine clearance value <or= 50 mL/min is expected to result in exposure similar to that in patients with normal to mildly impaired renal function, and became the basis for this dose recommendation in the FDA approved indication in NHL and MM, when added to G-CSF for mobilization.

In a phase I trial evaluating single dose IV Plerixafor in healthy donors for stem cell harvest and use in allogeneic transplant, pharmacokinetic evaluation demonstrated that C_{max} following the 320µg/kg IV dose remained below 1.0 µg/mL whereas 400 µg/kg (N = 3) and 480 µg/kg (N = 3) doses resulted in C_{max} levels of 1.8-2.2 µg/mL.

Finally, chronic administration of Plerixafor has also been evaluated by continuous infusion for 10 days in HIV patients in an open-label dose escalation study with doses ranging from 2.5 to 160 μ g/kg/h [30]. In this study, a 10 day infusion was administered via infusion pump at 40mL/hour (daily solutions prepared by dilution of a 10 mg/mL solution of Plerixafor in 0.9% saline). Note that the total dose infused in this study was much higher than those doses proposed here (i.e., the highest dose over 4 weeks for our protocol will be 11,200 mcg/kg compared to 38,400 mcg/kg total for the highest cohort in the cited study). The median terminal elimination half-life was 8.6 hours (range: 8.1-11.1 hours). Cardiac toxicities were observed in the HIV+ patients dosed to achieve C_{max} levels above 2 μ g/mL.

Plerixafor for Stem Cell Mobilization

Plerixafor is a bicyclam small molecule that selectively and reversibly inhibits CXCR4. In preclinical and clinical studies it was found to lead to a rapid increase in circulating hematopoietic progenitor cells and mature lymphocytes.

In a phase I clinical trial conducted in healthy volunteers, a single dose of Plerixafor by SC injection (160 or 240 $\mu g/kg$) given alone or added to a mobilization regimen of daily G-CSF (10 $\mu g/kg$) for four days was shown to be generally safe and well-tolerated, as compared to a mobilization regimen consisting of G-CSF alone [31]. The most frequently reported AEs were injection site reactions, GI effects, paresthesias, and headaches. Plerixafor augmented CD34+cell mobilization by G-CSF on average 3.8 fold. More recently, the safety of Plerixafor administered as a single agent by injection was further explored in healthy volunteers at doses up to 480 $\mu g/kg$ [32]. No dose limiting toxicity was observed, and common adverse events were diarrhea, injection site erythema, perioral numbness, sinus tachycardia, headache, nausea, abdominal distention and injection site pain.

Similar to the experience in healthy volunteers, phase I evaluation of a single injection of Plerixafor (160 or 240 µg/kg) given to 13 cancer patients (MM, n=7; NHL, n=6) was well tolerated and only grade 1 toxicities were observed [33]. A rapid and statistically significant increase in the total WBC and PB CD34+ counts at both 4 and 6 hours following a single injection were noticed. The absolute CD34+ cell count increased from a baseline of 2.6 +/- 0.7/ µL (mean +/- SE) to 15.6 +/- 3.9/ µL and 16.2 +/- 4.3/ µL at 4 hours (P=.002) and 6 hours after injection (P=.003), respectively. The absolute CD34+ cell counts observed at 4 and 6 hours following Plerixafor were higher in the 240 µg/kg group (19.3 +/- 6.9/ µL and 20.4 +/- 7.6/ µL, respectively) compared with the 160 µg/kg group (11.3 +/- 2.7/ µL and 11.3 +/- 2.5/ µL, respectively).

Plerixafor was then studied for hematopoietic stem cell mobilization coupled with G-CSF for autologous stem cell transplantation. In a phase II, open label, crossover study in 25 patients with NHL and MM, patients received 3 days of G-CSF run-in, and then underwent mobilization with one regimen of either: (A) up to 4 days of 10 μ g/kg of G-CSF or (B) up to 4 days of 10 μ g/kg of G-CSF plus 160 μ g/kg of Plerixafor [34]. Patients were apheresed one hour after the dose of G-CSF alone or 6 hours after the morning G-CSF plus Plerixafor dose for up to 4 days to achieve a target of 5 x 10⁶ cells/kg. After a rest period, patients received 3 days of G-CSF run-in, followed by the opposite regimen (A after B or B after A) and were apheresed in the same manner. The purpose was to determine safety, apheresis yields, and transplantation success. After the initial 8 patients were dosed at 160 μ g/kg, the protocol was amended to increase the G-CSF run-in from 3 to 4 days, and the Plerixafor dose to 240 μ g/kg. Later, the protocol was further amended such that the G-CSF alone regimen was always used first. There was no drug-

Page 13 of 52

related SAE or unexpected AE. More patients achieved $\geq 5 \times 10^6$ CD34+ cells/kg after mobilization with Plerixafor plus G-CSF compared to G-CSF alone. Nine patients (8 NHL and 1 MM patient) who mobilized CD34+ cells poorly with G-CSF alone ($<1.6 \times 106$ CD34+ cells/kg) improved when mobilized with Plerixafor plus G-CSF, with all patients achieving $>2 \times 106$ CD34+ cells/kg (range: 2.78 to 13.6 CD34+ cells/kg). The median day of polymorphonuclear leukocyte (PMN) engraftment was Day 10 and Day 17 for platelets, when using cells collected by Plerixafor plus G-CSF. Durability of engraftment has been measured up to one year.

Two phase III, multi-center, randomized, double-blind, placebo-controlled, comparative trials examined the ability of Plerixafor (240 $\mu g/kg$) plus G-CSF (10 $\mu g/kg$) vs. placebo plus G-CSF (10 $\mu g/kg$) to mobilize CD34+ stem cells for autologous hematopoietic stem cell transplantation in patients with NHL (protocol 3101) and MM (protocol 3102), respectively. Patients were excluded if they previously attempted stem cell mobilization or received a prior stem cell transplant.

In 3101, the addition of Plerixafor to a G-CSF regimen significantly increased the proportion of patients with NHL who were able to mobilize minimum (2 x 10⁶ cells/kg) and target (5 x 10⁶ cells/kg) numbers of CD34+ cells for autologous transplant and allowed both targets to be reached in significantly fewer apheresis days [35]. In 3102, the addition of Plerixafor to a G-CSF regimen, compared with G-CSF alone, significantly increased the proportion of patients with MM who were able to mobilize the target (6 x 10⁶ cells/kg) number of CD34+ cells needed for autologous transplant and allowed this target to be reached in significantly fewer apheresis days [36]. In both trials, hematopoietic stem cells mobilized with Plerixafor + G-CSF were equally capable of prompt and durable PMN and PLT engraftment, compared to cells mobilized with G-CSF alone.

In the controlled Phase III studies in patients with NHL and MM (3101 and 3102), a total of 301 patients were treated in the G-CSF plus Plerixafor 240 µg/kg SC group and 292 patients were treated in the G-CSF plus placebo group. The safety profile of Plerixafor was consistent with that observed in previous mobilization studies and adverse events that occurred more frequently with Plerixafor than placebo were: insomnia, headache, dizziness, diarrhea, nausea, flatulence, abdominal pain, vomiting, abdominal distention, dry mouth, stomach discomfort, constipation, dyspepsia, hypoaesthesia oral, arthralgia, musculoskeletal pain, hyperhidrosis, erythema, injection site reactions, fatigue, and malaise [35, 36]. Overall, the AE data, combined with the laboratory and vital sign findings, indicate that Plerixafor 240 µg/kg, in conjunction with G-CSF for the mobilization and collection of CD34+ cells, is well-tolerated in patients with NHL or MM undergoing autologous stem cell transplant. No notable differences in the incidence of AEs were observed across treatment groups from chemotherapy/ablative treatment through 12 months post-transplantation.

Plerixafor has been studied in over 2000 human subjects in over 78 clinical trials which have encompassed healthy volunteers, HIV infected patients, multiple myeloma patients, lymphoma patients, and patients with a variety of other malignancies. Mozobil® (Plerixafor injection) has been approved by the FDA in combination with G-CSF to mobilize hematopoietic stem and progenitor cells (HSPCs) for collection and subsequent autologous transplantation in patients with non-Hodgkin's lymphoma (NHL) and multiple myeloma (MM) based on phase III studies. Several reports have recently indicated that Plerixafor can also be safely administered with G-CSF in the context of a chemotherapy-based mobilization regimen [37-41]. Finally, based on favorable pharmacokinetic observations in healthy volunteers, the impact of intravenous Plerixafor in stem cell mobilization for cancer patients is now under investigation. In

a phase I/II study, escalating doses of intravenous Plerixafor (up to 400 μ g/kg) alone or added to G-CSF were administered to 25 patients with NHL (n=15) or HL (n=10). In the phase I portion of the study, one dose-limiting toxicity (grade 2 chest pain) was observed at 320 μ g/kg and no grade 3/4 toxicities occurred at 400 μ g/kg. 24 of 25 patients (96%) met the goal collection of \geq 2.0 x 106 CD34+ cells/kg and 21 of 25 patients (84%) collected \geq 5.0 x 10⁶ CD34+ cells/kg in a median 1 day of pheresis, including 6 of 6 patients in the 400 μ g/kg cohort.

Impact on Graft Composition and Transplant Outcomes

Although collectively referred to as CD34+ progenitor or stem cells, the full repertoire and relative abundance of each cell type collected during PBSC harvest is thought to be governed by selection of the mobilization regimen. The relative importance of blood graft composition on hematopoietic reconstitution following autologous transplant has been recently reviewed [42]. A number of small studies indicate that cells mobilized with Plerixafor are phenotypically distinct from those derived through other mobilization approaches. In macaque, for instance, gene and micro-RNA expression profiling of Plerixafor-mobilized CD34(+) cells include more B-, T-, and mast cell precursors, whereas G-CSF-mobilized cells have more neutrophil and mononuclear phagocyte precursors [43]. When evaluated in both healthy donors and lymphoma patients, Plerixafor alone mobilizes more precursors of the plasmacytoid dendritic cell (pDC) lineage, relative to mobilization with G-CSF + Plerixafor or G-CSF alone. Authors hypothesize that stem cell products enriched in pDCs may lead to improved immunity in the recipient after transplant and reduced incidence of CMV. The impact of Plerixafor on DC graft composition was corroborated in MM and NHL patients mobilized according to the approved indication. In terms of DC subsets, grafts mobilized with P+G contained similar % of myeloid (MDC, Lin-CD11c+HLA-DR+CD123-) and BDCA3+ DCs. The percentage of plasmacytoid DCs (PDC; CD123+BDCA2+HLADR+) was significantly increased in the P+G grafts (median, 0.87% vs. 0.30%; p=0.002), leading to a significantly higher PDC/MDC ratio in the P+G group, 2.08 vs. 1.01, p<0.0001). It was also found that there were significantly more CD8+ IFN-gamma and TNF-alpha secreting T cells in the P+G group as compared to the G group (median, 12.3% vs. 5.3%, p=0.01; and 5.9% vs. 2.8%, p=0.02, respectively). Again, more pDC cells, as well as CD34+CD45RA-CD123hi cells of unknown function, were also noted when Plerixafor was given intravenously at high doses with G-CSF, relative to G-CSF alone. Lastly, the addition of Plerixafor to G-CSF not only potentiates CD34+ peripheral stem cell yields, but also significantly increases the proportion of more primitive CD34+ CD38- subsets relative to G-CSF alone mobilization [44-46], the latter speculated to potentially promote superior engraftment after high-dose chemotherapy [47].

